5.2 EXCLUSION CRITERIA

Potential subjects will not be enrolled in the study if any of the following criteria are met:

1. The subject was previously randomized and treated under this clinical study protocol.
2. The study ulcer has:
 - a. Unexplored tunneling,
 - b. Undermining and/or
 - c. Sinus tracts

- that necessitates surgical operating-room debridement and/or penetrates to capsule/tendon/bone.
3. The subject has a known sensitivity to ethanol.
 4. The subject has a known allergy to bovine collagen.
 5. The subject has a known hypersensitivity to any of the components of the Apligraf agarose shipping medium listed below:
 - agarose,
 - L-glutamine,
 - hydrocortisone,
 - human recombinant insulin,
 - ethanolamine,
 - O-phosphorylethanolamine,
 - adenine,
 - selenious acid,
 - DMEM powder,
 - HAM's F-12 powder,
 - sodium bicarbonate,
 - calcium chloride
 6. The subject has a known sensitivity to any of the SOC materials which come in contact with the skin:
 - Coban™
 - Conforming gauze
 - Optifoam® non-adhesive dressing
 - Normal Saline (liquid or gel)
 - Cotton Gauze
 - Normal saline (liquid & gel)
 - Non-adhering dressings
 - Steristrips
 7. The subject is unable to safely ambulate with the use of a study required offloading boot.
 8. The subject has suspected or confirmed gangrene or wound infection of the study ulcer, as evidenced by tissue necrosis, redness, pain, and/or purulent drainage and/or receiving systemic antibiotics for the treatment of such.
 9. The subject has suspected or confirmed osteomyelitis of the foot with the study ulcer.
 10. The subject has participated in another clinical trial involving a device or an investigational study drug/treatment within 28 days of randomization.
 11. In the opinion of the Investigator, the subject has received, within 28 days of signing the Informed Consent Form, or is scheduled to receive during study participation, a medication or treatment which is known to interfere with or affect the rate and quality of wound healing (e.g., systemic steroids, immunosuppressive therapy, autoimmune disease therapy, dialysis, radiation therapy to the foot, vascular surgery, angioplasty, or thrombolysis).
 12. The subject has a history of bone cancer or metastatic disease of the affected limb, radiation therapy to the foot, or has had chemotherapy within the 12 months prior to signing the Informed Consent Form for trial participation.
 13. The subject is currently pregnant or is actively trying to conceive. (Patient statement confirming lack of pregnancy is sufficient.)

14. In the opinion of the Investigator, the subject is unable to comply with the treatment regimen (i.e., return for clinic visits, perform required dressing changes and use study-designated offloading device[s]).
15. In the opinion of the Investigator, the subject has a history of, or is currently diagnosed with, any illness or condition, other than diabetes, that could interfere with wound healing (e.g., end-stage renal disease, severe malnutrition, liver disease, aplastic anemia, Raynaud's Syndrome, connective tissue disorder, acquired immune deficiency syndrome, HIV positive, or sickle cell anemia).
16. In the opinion of the Investigator, the subject has unstable Charcot foot or Charcot with bony prominence that could inhibit wound healing.
17. The subject has ulcers secondary to a disease other than diabetes (e.g., vasculitis, neoplasms, or hematological disorders).
18. In the opinion of the Investigator, the subject has excessive lymphedema that could interfere with offloading and/or wound healing.
19. The study ulcer has received wound dressings that include growth factors, engineered tissues, or skin substitutes within 28 days of randomization or is scheduled to receive treatment during the study (e.g., PriMatrix, AMNIOEXCEL (first generation), Regranex, Dermagraft, EpiFix, GraftJacket, OASIS, Omnigraft, or Integra BMWD).
20. The study ulcer closed more than 30% in area, *post-debridement*, between Screening Visit 1 and Randomization (Day 0, as measured by planimetry).

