5.4 SCREEN FAILURES AND RESCREENING

Screen failures are defined as subjects who consent to participate in the clinical trial but are not subsequently randomized to a study intervention. A minimal set of information is required to ensure transparent reporting of screen failure subjects, to meet the Consolidated Standards of Reporting Trials (CONSORT) publishing requirements and to respond to queries from regulatory authorities. Minimal information includes demography, screen failure details, eligibility criteria, and any serious adverse events (SAE).

Individuals who do not meet the criteria for participation in this trial (screen failure) because of inability to attend second screening visit, recent participation in a former clinical trial, or remission of exclusionary cancer status as described in the exclusion criteria may be rescreened once. Rescreened subjects will be assigned a different subject number from the one designated at the initial screening.

The enrollment and screening flow chart of activities can be seen in figure 2. NOTE: Patients who enter the Screening Period will also be designated as a screen fail if they withdraw consent.

Figure 2: Screening Flow of Activities

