6.3 MEASURES TO MINIMIZE BIAS: RANDOMIZATION AND BLINDING

This study will use randomization to minimize bias in this open label study. Randomization will occur in a 1:1:1 ratio and use a mixed block methodology. No blinding is possible. As well, no analytical blinding will occur during data review and/or analysis.

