7.2 SUBJECT DISCONTINUATION/WITHDRAWAL FROM THE STUDY

Subjects are free to withdraw from participation in the study at any time upon request. As well, an investigator may discontinue or withdraw a subject from the study for the following reasons:

- If the subject's wound is open at follow-up week 1, the subject will be exited. They will be noted as having completed their study requirements.
- Significant study intervention non-compliance
- If any adverse event (AE), laboratory abnormality, or other medical condition or situation occurs such that continued participation in the study would not be in the best interest of the subject

- Anytime continued participation in the study is not in the best interest of the subject
- Disease progression which requires discontinuation of study participation
- Signs/symptoms of infection which require antibiotic therapy that persist more than 1 visit at a time or more than twice (non-consecutive visits) during the 12-week Treatment Phase.
- If the subject meets an exclusion criterion (either newly developed or not previously recognized) that precludes further study participation
- If the subject's site withdraws from the study
- If the Sponsor decides to stop the study

The reason for subject discontinuation or withdrawal from the study will be recorded on the appropriate eCRF. Subjects who sign the informed consent form and are randomized but do not receive the study intervention may be replaced.

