Important: If the subject has been randomized to the Apligraf cohort, the non-adherent layer should not be removed at Week 1 (See section 6.1.2.3 RECOMMENDED INSTRUCTIONS FOR USE OF APLIGRAF). Sites do not need to image the wound at Week 1 if the subject is in the Apligraf cohort; however, if the non-adherent layer disengages from the wound of its own volition, imaging may occur. In this latter case, care should be taken to not disturb the Apligraf.

- **Ulcer Assessments**

- **Screening Visits 1 & 2**

- The location of the ulcer will be noted. Extent of ulceration (i.e., tunneling, tendon exposure, etc.), exudate assessment, and infection assessment. **Ulcer area will always be assessed using the post-debridement (or pre-debridement if no debridement was performed) photographs.**

- **All Study Visits following Screening Visits 1 & 2**

- Exudate assessment, infection assessment, and investigator assessment of wound closure will be collected.

- **Completion of Study Assessment (Follow Up Visits)**

- Sites will assess completion status of the subject and will make a determination about the status of the wound (closed or not).

- **Standard of Care, Offloading (Screening Visits 1 & 2, Randomization, Weeks 1-11 as applicable)**

- Sites will apply SOC materials and boots according to the procedures laid out in section 6.1.2 and will document in the EDC system what materials were used. The site will document that a weekly kit was used and that they provided materials and training to the subject as applicable.

- **Randomization (Day 0)**

- Sites will review eligibility criteria a final time and document that the subject has met these criteria in the EDC system. The EDC system will provide the site with the appropriate cohort based on a pre-determined randomization scheme. The site will proceed with applying the appropriate treatment products based on the mandated cohort for that subject.

- **Investigational Product, Offloading (Randomization, Weeks 1-11, as applicable)**

- Sites will apply investigational product and SOC materials and boots, if applicable, according to the procedures laid out in section 6.1.2 and will document in the EDC system what materials were

used. Sites will document the product used (AMNIOEXCEL Plus or Apligraf), the product's lot number, and method of securing. The site will also document that a weekly kit was used, that they provided materials and training to the subject as applicable.

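### Exclusion 1 does not cover a subject who was randomized but not treated, and no section says that each person is randomized only once

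*Protocol*

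**What the plan says.** Exclusion 1 in Protocol section 5.2 reads: "The subject was previously randomized and treated under this clinical study protocol". The synopsis carries the same rule and sets the joining word in italics.

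Three other places bear on re-entry:

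- **Section 5.4** defines who may be rescreened: "Screen failures are defined as subjects who consent to participate in the clinical trial but are not subsequently randomized to a study intervention". One rescreen is allowed, for three listed reasons: a missed second screening visit, recent participation in an earlier trial, or remission of an exclusionary cancer. On identity it adds: "Rescreened subjects will be assigned a different subject number from the one designated at the initial screening".
- **Section 7.2** says: "Subjects who sign the informed consent form and are randomized but do not receive the study intervention may be replaced".
- **Section 7.3** says that subjects who are discontinued, lost or withdrawn without closure by week 12 are not replaced.

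On allocation, section 6.3 says: "This study will use randomization to minimize bias in this open label study". It adds: "Randomization will occur in a 1:1:1 ratio and use a mixed block methodology". Under Randomization (Day 0), section 8.2 says: "The EDC system will provide the site with the appropriate cohort based on a pre-determined randomization scheme". Section 8.1.3 lists randomization as step 6 of that visit and treatment as step 7.

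Protocol section 9.3 and SAP section 8.1 limit the ITT set to randomized subjects with at least one application of study intervention. The synopsis defines it as all randomized subjects.

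**The concern.** Exclusion 1 is the protocol's only eligibility rule on earlier participation in this trial. By requiring treatment as well as randomization, it leaves out exactly the people who stopped between the two steps. In an open-label trial, that is the point at which the arm is known and nothing has yet been applied.

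The arms differ visibly in burden: after randomization only SOC subjects continue daily home dressing changes (sections 5.3 and 6.1.2.1). A subject or site with a preference could therefore decline an unwanted arm, and exclusion 1 would not stop a second attempt. If this happened, membership of the arms would partly reflect preference, and prognosis may go with preference. Both primary contrasts, AMNIOEXCEL Plus against SOC and against Apligraf, rest on randomization for their validity.

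**Working it through.** This is mainly a comparison of text. The plan's one design figure, the 13.5% half width in section 9.2, is reproduced by 1.96 × √(2 × 0.9 × 0.1 / 38) = 13.49%, the value for a difference between two arms of 38. It does not enter the argument, and the fix leaves it unchanged.

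**Step 1. Does any exclusion catch a randomized, untreated person?** Exclusion 1 does not, because one of its two conditions is missing. Exclusion 10 concerns a different trial. Exclusion 19 requires earlier use of growth factors, engineered tissues or skin substitutes on the ulcer. Exclusion 14 depends on the Investigator judging the subject unable to comply. None clearly bars this person.

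**Step 2. Does any section give such a person a way back in?** Section 5.4 does not. It covers only consented subjects who were not randomized, and its three reasons do not include being randomized and untreated.

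**Step 3. What does section 7.2 add?** It allows replacement without saying by whom. It also sits uneasily with section 7.3: a subject who withdraws on seeing the arm is both randomized and untreated (may be replaced) and withdrawn without closure (not replaced).

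**Step 4. Is it clear who counts as treated?** Not in the SOC arm. Every subject receives SOC during screening. The Standard of Care row of the schedule is blank at Day 0 (Protocol Table 2, SAP section 4.2), although section 8.1.3 lists SOC treatment at that visit.

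**Step 5. What happens to the refused allocation in the analysis?** Under Protocol section 9.3 and SAP section 8.1 it is excluded, since no application was made. Under the synopsis it is kept.

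**Step 6. Could a second entry be traced?** Section 5.4 gives rescreened subjects a new number, and no link to the earlier number is described.

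**Step 7. Illustration of one re-draw.** Assume independent 1:1:1 draws and a single re-draw after an unwanted SOC allocation.

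- Chance of an allograft with one draw: 2/3 = 66.7%.
- Chance with one re-draw after SOC: 2/3 + (1/3 × 2/3) = 8/9 = 88.9%.

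The mixed blocks make draws dependent. Block sizes are not given, so the exact figure cannot be computed.

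**Step 8. Number of subjects, assumed range only.** If 5%, 10% or 20% of the 38 subjects expected in SOC were re-drawn once, that would be 38 × 0.05 = 1.9, 38 × 0.10 = 3.8 or 38 × 0.20 = 7.6 subjects. The documents give no rate, so these show scale and are not estimates.

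**The case against.** The strongest reply is that failing to meet an exclusion is not permission to enter. The only re-entry route described is section 5.4, and a randomized subject does not fit it. The ordinary meaning of replacement in section 7.2 is another person. This stands to the extent that the plan does not authorize re-randomization, and a reader who inferred that it does would go beyond the text. But 5.4 sets out what screen failures may do; it does not prohibit anything for others. The second condition in exclusion 1 has an effect only if some previously randomized people remain eligible.

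Other safeguards also narrow the gap. Inclusions 2 and 8 require willingness to follow the dressing regimen, and exclusion 14 may bar someone who cannot. Subjects have already done daily dressings during screening, treatment follows randomization at the same visit, and a second entry would need the ulcer to qualify again on size, duration and the 30% closure limit. These make the route narrow without closing it. They do little where the preference is the site's, or where the refused arm is an allograft.

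Three stronger readings are tempting but not supported:

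- *Allocation concealment is defeated.* Under section 10.1.8.1 the sponsor's teams hold the code and the EDC releases the arm only after eligibility is met. Concealment before assignment is intact; the exposure comes after the arm is shown.
- *The same person would be counted twice in the primary analysis.* Under Protocol section 9.3 and SAP section 8.1 the untreated first entry drops out. Double counting could arise only under the synopsis definition of ITT.
- *Closure rates would shift by several points.* One subject in 38 is 1/38 = 2.6 points, but that is the weight of any single subject. A larger figure needs an assumed number of re-drawn subjects, all moving the rate the same way. Under the plan's own assumption of 90% closure in every arm, the expected shift is about zero unless those who re-draw differ in prognosis.

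The italics are weak evidence of intent: in the text available they show in the synopsis but not in section 5.2.

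**Conclusion.** The point holds as an inconsistency that leaves a route open. Exclusion 1 does not bar a randomized, untreated person, section 5.4 provides no way in for that person, section 7.2 is silent on who the replacement may be, and nothing forbids a second randomization. Combined with open-label disclosure before treatment and an ITT set that drops untreated subjects, an allocation could be refused, re-drawn and lost from the primary analysis.

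Its effect on the results cannot be sized. Frequency is unknown, the documents do not show that re-entry occurred, and no change in closure rate follows from them. The move from 2/3 to 8/9 describes one subject's chance under independent draws and is not an estimate of bias. The correction is still worth making, because it changes a stated eligibility rule that protects the randomization.

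**What to change.** - **Exclusion 1, section 5.2 and synopsis:** delete the words on treatment, so that the exclusion applies to anyone already randomized in this trial.
- **Section 5.4:** state that rescreening applies only before randomization and that each person is randomized once.
- **Section 7.2:** state that a replacement is a different person who takes the next allocation, and that the subject replaced keeps the first allocation. Reconcile this with section 7.3.

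The conflicting ITT definitions need their own correction. Until that is made, report by arm the number randomized but not treated, with reasons.

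SAP section 12 says the photograph review data have already been collected and evaluated, so a wording change may come too late to affect enrolment. In that case, check the randomization records for any person entered twice and report the result, even if it is none.

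The cost is a two-word deletion in two places and a sentence or two in each of two sections. The 114 total, the 38 per arm and the 13.5% half width are unchanged. The downside is that a very few willing subjects, untreated for reasons unrelated to their allocation, could not re-enter.

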5.3 LIFESTYLE CONSIDERATIONS

Similar to patients experiencing SOC procedures outside of this study, subjects in this study will have to:

- Wear an offloading boot. This may cause subjects to ambulate with a limp or may reduce the subject's ability to perform activities they are used to doing (e.g., walk upstairs, go outside, etc.)
- Change dressings on a daily basis when in the Screening Period and if randomized to the SOC cohort. This may add time to a subject's daily grooming regimen.

All of these activities are similar to treatments/procedures that occur outside of this study and would occur whether or not this subject was included in the study.

[figure not shown]
5.4 SCREEN FAILURES AND RESCREENING

Screen failures are defined as subjects who consent to participate in the clinical trial but are not subsequently randomized to a study intervention. A minimal set of information is required to ensure transparent reporting of screen failure subjects, to meet the Consolidated Standards of Reporting Trials (CONSORT) publishing requirements and to respond to queries from regulatory authorities. Minimal information includes demography, screen failure details, eligibility criteria, and any serious adverse events (SAE).

Individuals who do not meet the criteria for participation in this trial (screen failure) because of inability to attend second screening visit, recent participation in a former clinical trial, or remission of exclusionary cancer status as described in the exclusion criteria may be rescreened once. Rescreened subjects will be assigned a different subject number from the one designated at the initial screening.

The enrollment and screening flow chart of activities can be seen in figure 2. NOTE: Patients who enter the Screening Period will also be designated as a screen fail if they withdraw consent.

Figure 2: Screening Flow of Activities

5.5 STRATEGIES FOR RECRUITMENT AND RETENTION

RECRUITMENT

Pre-screening activities for this study should include identification of potential subjects that meet the following general criteria.

- Age \geq 21 years,
- a diagnosis of diabetes and
- presence of DFU.

Note: pre-screening activities should never include the collection of study-related information or protected health information (PHI).

Advertisements are not prescribed for this study, per se; however, Integra may approve site-specific advertisements if warranted. Any site-specific advertisements must be approved by both the Sponsor and the site's Institutional Review Board prior to distribution to outside parties.

RETENTION

Investigators and site staff should make every effort to retain enrolled subjects and reduce loss-to-follow-up. The following methods should be employed in order to prevent subject loss:

- Ensure complete understanding of the roles and responsibilities of the study subject. This can be achieved with a thorough informed consent process.
- Make follow-up appointments far in advance
- Develop a strong rapport with study subjects, offer flexible appointment times, and ensure strong PI involvement

[Intentionally Blank]

6 STUDY INTERVENTION

6.1 STUDY INTERVENTIONS ADMINISTRATION

6.1.1 STUDY INTERVENTION DESCRIPTIONS

6.1.1.1 INVESTIGATIONAL PRODUCTS (to be used with SOC products)

AMNIOEXCEL Plus

AMNIOEXCEL Plus tri-layer Placental Allograft Membrane (T-PAM) is a minimally manipulated placental membrane product made from tissues donated by pre-screened mothers during planned C-sections. AMNIOEXCEL Plus is intended for use as a wound covering. This product is an allograft tissue intended for homologous use for the repair, reconstruction, and replacement of skin at the direction of a physician.

More information can be found in the supplied Instructions for Use document that is included with the AMNIOEXCEL Plus product.

In this study, AMNIOEXCEL Plus will be applied weekly, in conjunction with SOC, as long as the ulcer remains open, or up to and including Week 11, whichever comes first. Note: In order to reduce the risk of complications, AMNIOEXCEL Plus should not be used in the presence of active infection. See Section 7.1 for instructions on treating infections as part of this trial.

Apligraf

Apligraf is a living, bi-layered skin substitute: the epidermal layer is formed by human keratinocytes and has a well-differentiated stratum corneum; the dermal layer is composed of human fibroblasts in a bovine Type I collagen lattice. While matrix proteins and cytokines found in human skin are present in Apligraf, Apligraf does not contain Langerhans cells, melanocytes, macrophages, lymphocytes, blood vessels or hair follicles.

Cells used in the manufacture of Apligraf are processed under aseptic conditions. The cells are originally derived from donated human neonatal male foreskin tissue. The foreskin donor's mother is tested and found negative for human viruses, including antibodies to Human Immunodeficiency Virus Types 1 and 2 (HIV-1 and HIV-2), Human Immunodeficiency Virus Type 1 (HIV-1), human T-lymphotropic virus types 1 and 2 (HTLV-1 and HTLV-2), Hepatitis A Virus (HAV), Hepatitis B Virus (HBV), Hepatitis B Surface Antigen (HbsAg), Hepatitis C Virus (HCV), West Nile Virus (WNV), Epstein-Barr Virus (EBV), Cytomegalovirus (CMV), and Syphilis. The fibroblast and keratinocyte cell banks which are the source of the cells from which Apligraf is derived are tested for human and animal viruses, retroviruses, bacteria, fungi, yeast, mycoplasma, karyology, isoenzymes, and tumorigenicity. The final product is tested for morphology, cell viability, epidermal coverage, sterility, mycoplasma, and physical container integrity.

Product manufacture also includes reagents derived from animal materials including bovine pituitary extract. All animal derived reagents are tested for viruses, retroviruses, bacteria, fungi, yeast, and mycoplasma before use. Bovine materials are sourced to minimize bovine spongiform encephalopathy (BSE).

Apligraf is also indicated for use with standard DFU care for the treatment of full-thickness neuropathic DFUs of greater than three weeks' duration which have not adequately responded to conventional ulcer therapy and which extend through the dermis but without tendon, muscle, capsule or bone exposure.

More information can be found in the supplied Prescribing Information that is included with the Apligraf product.

In this study, Apligraf will be applied weekly, in conjunction with SOC, as long as the ulcer remains open, or up to and including Week 11, whichever comes first. Note: In order to reduce the risk of complications, Apligraf should not be used in the presence of active infection. See Section 7.1 for instructions on treating infections as part of this trial.

CONTROL PRODUCTS (i.e., SOC)

The control treatment reflects SOC appliances and materials:

- Coban™
- Conforming gauze
- Optifoam® non-adhesive dressing
- Cotton Gauze
- Normal saline (liquid or gel)
- Non-adhering dressings
- Steristrips
- An offloading boot (Pneumatic Short Leg Walker), as appropriate

